### **Recruitment and Data Collection prior to Test date:**

Case:

- At the end of their appointment with one of the endometriosis specialists at the BC Women's Health Centre for Pelvic Pain and Endometriosis, the physician will ask the patient if they are interested in learning more about this research study (if the physician deems them acceptable to be included based on screening of inclusion and exclusion criteria). The physician will provide the patient a copy of the consent form to read at home and will ask the patient if [name] or her delegate can call them in the next couple of days. Physicians will emphasize that participation is optional and does not influence their health care.

- A poster introducing the study will also be available in the clinic waiting rooms.
- Potential participants will be encouraged, if they feel comfortable doing so, to discuss the consent form with family, friends, and/or their physician. The potential case participants will be given a minimum of 24 hours to review the consent form before being contacted by [name] or her delegate.
- [name] will collect the physician forms and will confirm that the interested potential case participants consented to the data registry. [name] will only give [name] the contact information of the potential case participants that consented to the data registry. During the first phone call, [name] or her delegate will ask if the potential case participant is interested in participating in the study, and will explain the study and consent process, if they wish. During this phone conversation, [name] will remind the potential case participant that they have consented to the data registry, and consent to this study allows us access to analyze their data registry data. Verbal consent will be given if the potential case participant would like to participate, and a test appointment will be booked. [name] or her delegate will log the participant into the test computer during the test day so that they can complete the test day questionnaire online.
- Case participants will sign the consent form in-person at the beginning of the test day appointment.
- Note that the case participants do not need to complete the Data Registry questionnaire again, since we will be linking to their previously completed Data Registry questionnaires done before their physician appointment.

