#### Procedures for Data Collection (on Test day)

#### **Questionnaire:**

#### Case and Control:

- Data will be collected during a scheduled appointment with [name] or her delegate. The research visit will take approximately one hour of the participant's time (not including travel time to and from the site). The visit will take place in a BC Women's Health Centre private room (4th floor of the Shaughnessy building at the BC Women's Hospital). Data collected will include an online questionnaire containing: today's date, score of sexual and non-sexual pains, first day of last menstrual period, any changes in medication since their last visit to BC Women's Health Centre, current hormonal suppression, date of last physician appointment, menstrual cycle data, last time they have had sexual intercourse and how many times have they had sexual intercourse in the last one month. The pelvic pain questions asked on this online questionnaire are modified from the Brief Pain Inventory Short Form. This questionnaire will be filled out on REDCap online using a desktop computer in the room.
- The testing room will be maintained at a temperature between 20 and 25 degrees Celsius, with no fans or open windows (may use a white noise machine), and no stressful stimuli (e.g., no loud noises or blinking lights).
- As the participant completes the online questionnaire, [name] or her delegate will set up the Algometer and calibrate the force sensing resistor (FSR). [name] or her delegate will answer any questions.

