*“This instrument is called the Electronic Thimble Algometer and will be used today to measure your pain pressure threshold. The pain pressure threshold is when the sensation of pressure changes to the first sensation of pain. During this test I will place this part of the instrument, called the force sensing resistor, on the end of my index finger and will apply a constant pressure to your right shoulder, left shoulder, right first dorsal interosseous muscle and your left first dorsal interosseous muscle. The pain-pressure threshold measurement from these four sites will be duplicated. The order of the test sites will be determined randomly. I will constantly apply pressure to the test site until you click on the mouse indicating that the sensation of pressure has changed to the sensation of pain. Please click the mouse at your first sensation of pain. There will be a thirty second break between each test site, and then a two minute break before duplicating the test. You will hear the prompt for the next test site after each of the breaks. If at any time you are no longer comfortable or change your mind about participating, please let me know. I will then stop the testing immediately. Do you have any questions before we begin?”*

This script will be read to each participant before the test begins. Any questions or concerns they have will be answered to the best of the investigators ability and/or addressed before they willingly partake in this test.

- The participants will be blinded to the computer screen (where the PPT data is shown) to ensure they are not influenced by the data during the QST
- The observation made by this QST is that a lower PPT is suggestive of increased central sensitization.
- After testing the individual will remain in the test room until she feels ready to leave.

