No participant data will be stored on the test laptop. The PPT data will be written down on a paper copy with the participant's unique study ID at the top to link them to their REDCap data. The paper copy will be entered into an encrypted file on a PHSA secure computer. All paper data will be placed in a confidential file box and shredded as per hospital policy. If needed, computer files will be deleted according to UBC policy 85.

The data from the survey can be viewed by [name] or her delegate via REDCap; therefore, there is no risk of disclosure of information by unsecured email servers.

All researchers in this study have been trained in the proper protocol for privacy and confidentiality, including completion of the Tri-Council Policy Statement: Ethical conduct for Research Involving Humans (TCPS-2 CORE) and a Privacy and Confidentiality course provided by PHSA.

---

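### The tester who presses by hand for the PPT is in the room while pain scores are entered, and no rule keeps those scores from the tester until the readings are done

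*Combined protocol and SAP*

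**What the plan says.** In Procedures for Data Collection (on Test day), Questionnaire, one role runs the visit: "Data will be collected during a scheduled appointment with [name] or her delegate". The participant starts with a form that includes "score of sexual and non-sexual pains, first day of last menstrual period". On where this happens, the section says "This questionnaire will be filled out on REDCap online using a desktop computer in the room". It then adds: "As the participant completes the online questionnaire, [name] or her delegate will set up the Algometer and calibrate the force sensing resistor (FSR". The same role answers questions at this stage. For cases, the recruitment section says that this role "will log the participant into the test computer during the test day so that they can complete the test day questionnaire online".

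PPT testing follows the questionnaire. In the script under Quantitative Sensory Testing (QST), the speaker puts the sensor, "called the force sensing resistor, on the end of my index finger", and presses until the participant clicks the mouse at the first pain. Four sites are tested twice, giving eight readings. The device sets the site order at random, the script is read to everyone, breaks are timed, and the equipment is calibrated. Readings are written on paper under the study ID.

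The only blinding stated is this: "The participants will be blinded to the computer screen (where the PPT data is shown". No section masks the tester to pain scores, clinical history or group. Data Analysis specifies a Spearman correlation of PPT with deep dyspareunia among the cases.

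**The concern.** The primary analysis correlates two quantities that should be measured independently of each other. Here the pain scores come first, with the future tester in the room, and the PPT comes second, by a manual procedure for which the plan gives no rate of force increase. The protocol also states the expected direction: more severe deep dyspareunia goes with a lower PPT.

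The participant's click ends each reading, but the tester decides how the force rises towards it. Suppose a tester presses more slowly on a woman believed to have severe pain. Less force then accumulates between first pain and the click, and the reading is lower. That would produce a correlation in the hypothesised direction without any sensitization; a different habit could push it the other way. A larger sample does not remove such a bias, and neither calibration nor random site order acts on it.

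The plan already treats influence during QST as a threat, since it hides the screen from the participant. It leaves the tester's side open.

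**Working it through.** **What the text establishes and what it leaves to inference**

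- Stated: the visit is run by the researcher or a delegate, who is present and answering questions while the form is filled in; the form contains pain scores; PPT comes afterwards, by hand.
- Close inference: the person in the room is the one who presses. The script's speaker is called the investigator, and no second staff member is mentioned.
- Not stated: that the tester looks at the answers, or is kept from doing so.

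**Which outcome score is exposed**

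The plan does not say which deep dyspareunia score enters the primary correlation.

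- Test-day score: entered just before PPT, in the tester's presence. This is the direct route.
- Registry score: completed before the physician appointment. Routine tester access before testing is not shown.
- Diary score (Online Survey, Appendix C): collected over the six weeks after testing, so it cannot be known while pressing. Bias could act only through earlier scores that predict it. If the tester responds to the earlier score alone, the spurious correlation is multiplied by roughly the correlation between the two scores, so it is smaller.

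**The plan's own figure**

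Inputs from Data Analysis: 126 cases, power 0.80, alpha 0.05 two-tailed. No effect size is given, so 126 cannot be reproduced. It can be back-solved with Fisher's z, taking v = 1 for the Pearson variance or v = 1.06 for the Spearman variance:

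r = tanh[(1.960 + 0.842) × √(v/(126 − 3))]

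- v = 1: 2.802/√123 = 0.2526, so r = 0.247.
- v = 1.06: 0.2526 × √1.06 = 0.2601, so r = 0.254.
- Smallest significant |r|, tanh[1.960 × √(v/123)]: 0.175 and 0.180.

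**How small a bias would matter (illustration under assumption)**

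Suppose there is no true association and the tester induces a correlation ρ. With δ = atanh(ρ) × √(123/v), the two-sided rejection probability is Φ(δ − 1.960) + Φ(−δ − 1.960). For ρ = 0.10 and v = 1, δ = 0.1003 × 11.09 = 1.113, which gives 0.198 + 0.001 = 0.200.

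| Assumed ρ | Fisher z, v = 1 | Fisher z, v = 1.06 | Simulated Spearman test |
|---|---|---|---|
| 0 | 5% | 5% | 4.7% |
| 0.05 | 8.6% | 8.4% | 7.4% |
| 0.10 | 20.0% | 19.1% | 17.8% |
| 0.15 | 38.8% | 37.0% | 36.2% |

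The simulation used 4,000 runs per row and normally distributed values. PPT was lowered by 0.05, 0.10 or 0.15 residual SD per SD of pain score. The mean Spearman coefficients were −0.046, −0.094 and −0.142, slightly below the nominal ρ in size, which partly explains the lower rates. A shift of 0.25 gave a mean of −0.229 and 73.8% rejection, close to the effect that 126 cases can detect. The documents give no value for the shift.

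**The case against.** The strongest reply is that nothing shows the tester seeing a score. During the questionnaire the tester is occupied with calibration; the form is on a desktop, while the algometer feeds a laptop; and logging a participant in comes before any score exists. The person who phones cases is given only their contact information, and registry data are released by a coordinator on request (Data Linking). The participant ends each reading, and the script, timed breaks, random order and duplicate readings leave the tester limited freedom. All of this stands, and it limits the risk. It does not amount to masking, because the plan contains no rule that would stop a glance at the screen or a question about a pain item from revealing the score.

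Four stronger readings are tempting, and the documents do not support them.

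- *The tester has REDCap access to the test-day scores.* Ethical Considerations says "The data from the survey can be viewed by [name] or her delegate via REDCap". The survey there may mean the six-week diaries, which come after PPT; Data Storage lists questionnaires and daily surveys separately. The terms are not used consistently, so the sentence proves neither reading.
- *Knowledge of case or control status biases the primary result.* The analyses are within cases (Design). Group status bears only on the case-control comparison, and the controls serve mainly for troubleshooting.
- *Variation between testers takes power below 0.80.* The 126 was derived from data on 30 cases. If they were tested under this procedure, that variation is already in the estimate.
- *No tester identifier is recorded.* The PPT form is not reproduced; the text mentions only the study ID.

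**Conclusion.** The point holds as a missing safeguard. The plan does not keep the tester from the test-day pain scores before a manual measurement that will be correlated with pain. It would be wrong to conclude that bias has occurred, or that the primary correlation is invalid.

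The size of any bias is unknown. The tabulated rejection rates restate an assumed spurious correlation as an error rate; they do not estimate this study's false-positive rate. They show only that a correlation well below the roughly 0.25 the study can detect would be enough to matter. The conclusion assumes that the person in the room is the tester, and it is weakest if the diary score proves to be the primary outcome. This is a cheap improvement, worth making because masking cannot be restored after the data are collected.

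**What to change.** In the Questionnaire and QST sections:

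1. Require that the tester not view a participant's test-day pain answers, or earlier screening or registry pain answers, until all eight PPT readings for her are recorded. Turn the questionnaire screen away from the tester, have the participant submit the form herself, and withhold the tester's REDCap view of the pain forms until the PPT record is closed.
2. Put a tester code on the PPT form. If more than one person tests, add a sensitivity analysis of the primary association adjusted for tester. This deals with differences between testers; it does not detect or correct expectation bias.
3. State, as a limitation of the secondary case-control comparison only, that the tester is not masked to case or control status.

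Masking works on the tester's knowledge. With the score unknown, variation in pressing adds noise but is no longer tied to that score. A tester might still form an impression from conversation, so the most direct route is closed but not every route.

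The cost is one access setting, a room-layout rule and one form field, with no extra staff and no change to the sample size or the primary test. The downside is that questions about a pain item must be answered without looking at the answers.

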#### Quantitative Sensory Testing (QST):

##### Case and Control:

- After the questionnaire has been completed, the participants will undergo QST to measure their pressure-pain threshold (PPT), the point where the sensation of pressure has changed to the sensation of pain (or first report of discomfort). This procedure will take approximately 30 minutes. Before testing begins, it will be made clear that the participants can withdraw from the study even during the procedure if they find it too uncomfortable.
- The PPT data will be written down on a paper copy with the unique study ID, and entered into an encrypted excel file.
- The testing room will be at a temperature between 20 and 25 degrees Celsius, with no fans or open windows, and no stressful stimuli (e.g., no loud noises or blinking lights). The participants will be sitting on a chair when QST occurs and before testing they will be asked if they are comfortable.
- QST, to measure PPT, will be done using an Electronic Thimble Algometer (purchased from the University of North Carolina). The Electronic Thimble Algometer consists of a calibration load cell and a force sensing resistor (FSR), as well as an amplifier which "reads" the force from the resistor and transfers the data to the connected computer (a laptop). The calibration load cell will be calibrated using 2 weights (0kg and 0.5kg) (Fisher Scientific, Cat #:S01369), as per the manufacturers recommendations. The FSR will then be calibrated on the load cell. The calibrations will ensure the accuracy and reliability of the measurements. Four test sites will be measured: left deltoid muscle, right deltoid muscle, and left first dorsal interosseous muscle and right first dorsal interosseous muscle. All test sites will be measured twice; therefore, the PPT will be measured eight times. The test sites will be measured bilaterally and duplicated to obtain an average value. The order of the test sites will be measured randomly (done automatically by

the Electronic Thimble Algometer). The investigator will describe the process of this test to the participant, following this script:

*“This instrument is called the Electronic Thimble Algometer and will be used today to measure your pain pressure threshold. The pain pressure threshold is when the sensation of pressure changes to the first sensation of pain. During this test I will place this part of the instrument, called the force sensing resistor, on the end of my index finger and will apply a constant pressure to your right shoulder, left shoulder, right first dorsal interosseous muscle and your left first dorsal interosseous muscle. The pain-pressure threshold measurement from these four sites will be duplicated. The order of the test sites will be determined randomly. I will constantly apply pressure to the test site until you click on the mouse indicating that the sensation of pressure has changed to the sensation of pain. Please click the mouse at your first sensation of pain. There will be a thirty second break between each test site, and then a two minute break before duplicating the test. You will hear the prompt for the next test site after each of the breaks. If at any time you are no longer comfortable or change your mind about participating, please let me know. I will then stop the testing immediately. Do you have any questions before we begin?”*

This script will be read to each participant before the test begins. Any questions or concerns they have will be answered to the best of the investigators ability and/or addressed before they willingly partake in this test.

- The participants will be blinded to the computer screen (where the PPT data is shown) to ensure they are not influenced by the data during the QST
- The observation made by this QST is that a lower PPT is suggestive of increased central sensitization.
- After testing the individual will remain in the test room until she feels ready to leave.

### **Feedback Questionnaire:**

Case and Controls:

- After the participant's PPT has been measured, they will be given an anonymous feedback form to assess the procedure mechanisms and specifications, as well as comfort level before, during and after testing. This will allow investigators to adjust any necessary procedure details to create a more comfortable environment/test for future participants.

A mental health recourse sheet will be given to every participant at the end of the appointment. If the participant requires more support than [name] can provide, the participant will be directed to the clinic nurse. The clinic nurse will triage the participant and provide them with the level of care the participant needs. If it is an emergency situation, 911 will be called.

### **Procedures for Data Collection (after Test day)**

#### **Online Survey:**

Cases only:

- After recruitment and signing the consent form, case participants will be asked to record study data daily after their scheduled test date.
- REDCap surveys will be completed for six weeks after the test date, and data will be collected at the end of the six weeks. The data collected on the surveys for this study is shown in Appendix C.
- The data collected (shown in Appendix C), will allow for daily prospective pain scores, rather than retrospective recollections of pain scores.
- All case participants will receive daily notifications to complete the survey. Case participants will be sent one email reminder in the evening if they have not filled out the questionnaire that day. A Mental Health Crisis line number is given on the notifications in case the participant becomes distressed. At the end of the first week of entering the survey data, the participants will receive a phone call, from [name] or her delegate, to follow up on usage and any troubles or suggestions. Any problems will be addressed by [name].

Participants without email addresses will have the opportunity to complete the surveys on a printed out copy (given to them on the appointment day) and mail/bring in-person to the Centre at the end of the 6 weeks. Two weeks after the end of the study (after 6 weeks of survey entry), if the participant who completed their surveys on printed copies have not sent in their data, [name] or her delegate will call the participant to kindly remind them to mail/bring in the data.

The recruitment and procedures for this study are illustrated in Appendix A (Case) and Appendix B (Controls).

#### Data Linking:

The Data Registry for Chronic Pelvic Pain and Endometriosis (H16-00264) collects a wide range of data from all consenting patients of the BC Women's Centre for Pelvic Pain and Endometriosis including those who undergo surgery at the clinic. Case participants in this study (Endometriosis deep dyspareunia and central sensitization) are therefore also listed in the Data Registry (they consent to both). This will allow for direct matching. A data access request will be sent to the research coordinator ([name]) to collect the case participant data from the Data Registry. The information provided to the Data Registry research coordinator for data linking includes: unique study ID, MRN, PHN, first and last name, and date of initial visit to BC Women's Health Centre. All the data from the Data Registry is being linked. This data will be placed in an encrypted excel file on the O: drive. The research coordinator will pull the appropriate information and replace the participants Data Registry REDCap ID with the unique study ID for this study and place the file back on the O: drive, where [name] or her delegate will have access to it. Data for both studies are kept on the BC Women's secure O: drive in separate password protected folders with restricted access to study team members; therefore the data transfer can be undertaken within the PHSA secure network.

Once data linkage is complete the linking spreadsheet sent to the Data Registry research coordinator will be permanently deleted as per UBC policy 85.

